8.6.1. Case Report Forms/Data Collection Tools/Electronic Data Record

As used in this protocol, the term CRF should be understood to refer to either a paper form or an electronic data record or both, depending on the data collection method used in this study.

A CRF is required and should be completed for each included patient. The completed original CRFs are the sole property of Pfizer and should not be made available in any form to third parties, except for authorized representatives of Pfizer or appropriate regulatory authorities, without written permission from Pfizer. The investigator shall ensure that the CRFs are securely stored at the study site in encrypted electronic form and will be password protected to prevent access by unauthorized third parties.

The investigator has ultimate responsibility for the collection and reporting of all clinical, safety, and laboratory data entered on the CRFs and any other data collection forms (source documents) and ensuring that they are accurate, authentic/original, attributable, complete, consistent, legible, timely (contemporaneous), enduring, and available when required. The CRFs must be signed by the investigator or by an authorized staff member to attest that the data contained on the CRFs are true. Any corrections to entries made in the CRFs or source documents must be dated, initialed, and explained (if necessary) and should not obscure the original entry.

The source documents are the hospital or the physician's chart. In these cases, data collected on the CRFs must match those charts.

8.6.2. Record Retention

To enable evaluations and/or inspections/audits from regulatory authorities or Pfizer, the investigator agrees to keep records, including the identity of all participating patients (sufficient information to link records, eg, CRFs and hospital records), copies of all e-CRFs, safety reporting forms, source documents, detailed records of treatment disposition, and adequate documentation of relevant correspondence (eg, letters, meeting minutes, and telephone call reports). The records should be retained by the investigator according to local regulations or as specified in the clinical study agreement (CSA), whichever is longer. The investigator must ensure that the records continue to be stored securely for so long as they are retained.

If the investigator becomes unable for any reason to continue to retain study records for the required period (eg, retirement, relocation), Pfizer should be prospectively notified. The study records must be transferred to a designee acceptable to Pfizer, such as another investigator, another institution, or to an independent third party arranged by Pfizer.

Study records must be kept for a minimum of 15 years after completion or discontinuation of the study, unless or as required by applicable local regulations.

The investigator must obtain Pfizer's written permission before disposing of any records, even if retention requirements have been met.

8.7. Data Analysis

The anonymously collected data of each patient cohort will be analyzed with an exploratory data analysis approach. The de-identified dataset will be analyzed using statistical software. Descriptive

statistics, survival analyses, and exploratory methods will be employed to address study objectives. Outliers and data inconsistencies will be reviewed and addressed before final analysis. Only descriptive statistics will be reported and no effort to determine statistical significance will be made.

Hospitalization and emergency department admission rates attributable to chronic heart failure, as well as hospitalization rates for cardiovascular-related illness, will be expressed as events per patient-year to account for variable follow-up durations.

Overall survival will be described using the Kaplan–Meier method, appropriately accounting for differing follow-up times and censoring; competing risks will not be considered.

Cardiac and extra-cardiac “red flags,” together with clinical and functional outcomes, will be described using means (standard deviations) for continuous variables and proportions for categorical variables.

Missing data will not be imputed; all analyses will be based on available data, with the number of missing observations reported for each variable where applicable.

Detailed methodology for summary and statistical analyses of data collected in this study will be documented in a statistical analysis plan (SAP), which will be dated, filed, and maintained by the sponsor. The SAP may modify the plans outlined in the protocol; any major modifications of primary endpoint definitions or their analyses would be reflected in a protocol amendment.

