7. RESEARCH QUESTION AND OBJECTIVES

The aim of this study is to describe the clinical characteristics and outcomes of patients with ATTR amyloidoid cardiomyopathy (ATTR-CM) treated with tafamidis at a single center in Turkey.

Primary Objective:

- To describe the rate of hospitalizations and emergency admissions due to chronic heart failure in the patients treated with Tafamidis

Secondary Objectives:

- To describe the rate of cardiovascular-related hospitalizations and overall survival among patients treated with Tafamidis during Tafamidis exposure time period.
- To describe the presence of cardiac and extracardiac red flags (Extra-cardiac Red Flags: Carpal Tunnel Syndrome, Peripheral Neuropathy, Lumbar Stenosis, Renal Insufficiency, Cardiac Red

Flags: Elevated NT Pro BNP and troponin, Pseudo infarct Sign, Voltage Mismatch, Conduction Disorder, Increased Wall Thickness (Interventricular septum), Pericardial Effusion)) in patients with ATTR - CM treated with tafamidis during the baseline period prior to initiation of tafamidis treatment.

- To describe the clinical and functional outcomes in ATTR CM patients during the baseline period prior to tafamidis treatment and during the follow-up period of treatment with tafamidis such as HRQoL measures, concomitant medication, biomarkers (NT pro-BNP, troponin), echocardiographic parameters (6 min walk test, Kansas City Cardiomyopathy Questionnaire Score, Creatinine eGFR, Ejection Fraction, Interventricular Septum, E/A ratio, E/e' mean ratio, Tricuspid Regurgitation Velocity, Tricuspid Annular Plane Systolic Excursion).

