This study is a cohort study because it involves following a group of ATTR CM patients who share common characteristics (in this case, the target population managed by the specialized center) over a period. Since the ATTR CM is a progressive disease, a cohort design will allow longitudinal evaluation of clinical outcomes and progression as managed in real world clinical practice. The cohort design was chosen instead of different study designs because it allows for the longitudinal evaluation of clinical outcomes and disease progression in patients with ATTR amyloid cardiomyopathy (ATTR-CM), which is essential for understanding the impact of tafamidis treatment over time. This design leverages routinely collected data in Turkish clinical practice, ensuring the availability of relevant information and reflecting real-world settings. Additionally, the specialized center's expertise in managing ATTR-CM patients enhances the reliability and applicability of the study results.

Strength of the study is described in the [Section 9.7](#) (Strengths and Limitations of the Research Methods).

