8.2. Setting

One Turkish Centre involved in the diagnosis and management of patients affected by ATTR-CM will participate in the study. This Centre is selected according to their clinical and research expertise, in

addition to the number of patients they are used to routinely caring for. A clinical research organization (CRO) on behalf of Pfizer will support the regulatory and administrative procedures to get authorization and the operations at Centre needed for data collection.

After regulatory authorization and local contract finalization, the study will be started at Centre. The site Study Team, including the Principal Investigator and additional identified personnel (e.g., research nurse, clinical study manager) will be trained on the protocol and planned study procedures, in addition to the use of the study-specific eCRF. Study data will be collected according to [Section 9.1. Study Design](#) and [Figure 1](#) as patients are diagnosed with ATTR-CM between January 2023 and January 2025. For all patients, the 6-month period before the index date when tafamidis is started will be considered as the baseline period, and the relevant parameters will be collected from this period. Original data, routinely collected by means of specific tools (e.g., paper charts, electronic charts,) will be transferred to the eCRF by the Study Team in site.

Retrospective data from the patient's files/source data will be collected in the CRF up to the earliest date of: treatment discontinuation, death, lost to follow-up (the patient could not be observed and any more contacted at some time point during their follow-up) or end of the follow-up period of 30-Sep-2025 (inclusive). For the patients lost to follow-up, the end of their follow-up period will be the respective date of the last contact. In the case patients experience clinical events (e.g. hospitalization due to Chronic Heart Failure, safety event) starting before 30-Sep-2025 and continuing beyond end of the follow-up, the respective details until the end of the event should be included into the eCRF.

The CRO will ensure oversight and monitoring of the study at the site.

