Albumin	Patient Baseline Laboratory Parameters, Secondary Objective	Baseline Assessment Period	Continuous	Electronic health records or physical patient file	As recorded in the source data g/L, (10-200)
Modified BMI	Patient Baseline Laboratory Parameters, Secondary Objective	Baseline Assessment Period	Continuous	Electronic health records or physical patient file	(Albumin x BMI) (automatic calculation)
NT pro-BNP	Cardiac Red Flag, Functional Outcome, Secondary Objective	Baseline, Follow up Assessment Period	Continuous	Electronic health records or physical patient file	As recorded in the source data ng/L, (100-100000)
Troponin	Cardiac Red Flag, Functional Outcome, Secondary Objective	Baseline, Follow up Assessment Period	Continuous	Electronic health records or physical patient file	As recorded in the source data
Serum free light chain levels (Kappa) mg/L	Patient Baseline Laboratory Parameters, Secondary Objective	Baseline Assessment Period	Continuous	Electronic health records or physical patient file	As recorded in the source data mg/L, (5-1000)

Serum free light chain levels (Lambda) mg/L	Patient Baseline Laboratory Parameters, Secondary Objective	Baseline Assessment Period	Continuous	Electronic health records or physical patient file	As recorded in the source data mg/L, (5-1000)
Serum free light chain levels (Kappa/Lambda (automatic calculation))	Patient Baseline Laboratory Parameters, Secondary Objective	Baseline Assessment Period	Continuous	Electronic health records or physical patient file	free-kappa–lambda ratio (automatic calculation)
Serum immunofixation electrophoresis monoclonal gammopathy	Patient Baseline Laboratory Parameters, Secondary Objective	Baseline Assessment Period	Nominal	Electronic health records or physical patient file	As recorded in the source data yes/no
24h urine immunofixation monoclonal gammopathy	Patient Baseline Laboratory Parameters, Secondary Objective	Baseline Assessment Period	Nominal	Electronic health records or physical patient file	As recorded in the source data yes/no
Immunofixation/Immunoelectrophoresis monoclonal gammopathy	Patient Baseline Laboratory Parameters, Secondary Objective	Baseline Assessment Period	Nominal	Electronic health records or physical patient file	As recorded in the source data yes/no
Heart Rate	Patient Baseline ECG Parameters, Secondary Objective	Baseline Assessment Period	Discrete	Electronic health records or physical patient file	(BPM) Beat per minute, resting, as recorded in the source data

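### Section 8.7 fixes available-case mean (SD) for all continuous clinical and functional outcomes and names no same-patient comparison, so the apparent course on tafamidis can reflect who remains under observation; mean (SD) also suits NT-proBNP and troponin poorly, and typing KCCQ as ordinal points to proportions for a score.

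*Protocol*

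**What the plan says.** The third secondary objective (section 7) is to describe clinical and functional outcomes "during the baseline period prior to tafamidis treatment and during the follow-up period of treatment with tafamidis". Section 8.1 chooses a cohort design because "it allows for the longitudinal evaluation of clinical outcomes and disease progression in patients with ATTR amyloid cardiomyopathy", and adds "which is essential for understanding the impact of tafamidis treatment over time". Follow-up is quarterly.

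For these outcomes and the red flags, section 8.7 gives one rule: they "will be described using means (standard deviations) for continuous variables and proportions for categorical variables". On missing data it says "Missing data will not be imputed; all analyses will be based on available data, with the number of missing observations reported for each variable". It names no change from baseline, same-patient comparison, median or log scale for these outcomes.

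Section 8.2 collects data "up to the earliest date of: treatment discontinuation, death, lost to follow-up" or 30 September 2025. The reason given for an amendment in section 4 puts follow-up at about 6 to 30 months.

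In Table 1 (section 8.3), NT-proBNP is "As recorded in the source data ng/L, (100-100000"), assessed at baseline and follow-up. Troponin has the same assessment periods and no stated range. The 6-minute walk test and KCCQ are assessed at index and follow-up, and KCCQ is typed as ordinal.

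**The concern.** Three features of the stated rule work against the objective it serves.

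- **Changing patients.** Available-case means at successive quarters come from different sets of patients. Some have left because their calendar follow-up ran out, others through death, discontinuation or loss. If sicker patients leave sooner, the later means look better even when nobody has improved.
- **Skewed biomarkers.** NT-proBNP may legitimately span three orders of magnitude in this database. One high value can move a mean of 70 patients noticeably.
- **KCCQ type.** The rule offers only continuous or categorical handling. An ordinal variable falls most naturally under categorical, so a questionnaire score would be tabulated as proportions.

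At stake is how the before-and-during-treatment tables are read. The study has no comparator, so readers will look to these tables for the course on treatment.

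**Working it through.** The study is descriptive and the protocol states no figure to reproduce for this point. The protocol gives no exit rate, mortality, SD or NT-proBNP distribution, so everything below that needs one rests on an assumption.

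**1. How many patients can contribute.** Inputs: about 70 patients (abstract) and follow-up of about 6 to 30 months (section 4). Assumption: follow-up lengths are spread evenly over that range. The share reaching month t is (30 − t)/24.

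| Month | Share | Of 70 |
|---|---|---|
| 12 | 18/24 = 0.75 | 52.5 |
| 18 | 12/24 = 0.50 | 35 |
| 24 | 6/24 = 0.25 | 17.5 |

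This is before any death or discontinuation. The calendar cut-off shortens follow-up by start date and does not by itself favour healthier patients.

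**2. Shift of the mean with no true change.** Let z be baseline severity in SD units (standard normal) and let the exit hazard be h × HR^z. With no within-patient change, the apparent improvement at time t is −E[z·S(t|z)] / E[S(t|z)], where S(t|z) = exp(−h·t·HR^z). Both h and HR are assumed.

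| Yearly exit h | HR per SD | 18 months | 24 months |
|---|---|---|---|
| any | 1.0 | 0 | 0 |
| 0.05 | 1.5 to 2.0 | 0.03 to 0.06 SD | 0.04 to 0.08 SD |
| 0.25 | 1.5 to 2.0 | 0.15 to 0.26 SD | 0.20 to 0.33 SD |

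At h = 0.25, combined with the even spread in step 1, about 10 of 70 patients are left at 24 months.

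**3. The same on the NT-proBNP scale.** Simulated cohorts of 70 used an assumed log-normal distribution (median 3000 ng/L, log-SD 1.0), no within-patient change and a yearly exit hazard of 0.15.

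- Exit unrelated to baseline: the mean moves by less than 1%.
- Log hazard ratio 0.7 per SD: the mean falls from 4948 to 4188 at 12 months (4188/4948 − 1 = −15%) and from 4951 to 3647 at 24 months (−26%).
- In the same setting the median falls from 3035 to 2732 at 12 months (−10%). A median handles skew but does not remove selection.
- The within-patient geometric-mean ratio is 1.00 in every setting, as it should be when nothing changes.

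**4. Sensitivity of the mean to one value.** Take 69 patients at 3000 ng/L and one at the accepted maximum: (69 × 3000 + 100000)/70 = 4386, which is 46% higher. With one value of 30000 the mean is 3386, or 13% higher. The median stays at 3000 in both cases. For a log-normal with log-SD 1.0, the mean is exp(0.5) = 1.65 times the median and the SD is √(e − 1) = 1.31 times the mean, so mean ± SD would reach below zero.

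**The case against.** The strongest reply is that section 8.7 leaves detailed methodology to a SAP that is not shown and that may modify the plan. The protocol neither says that baseline and follow-up will be compared as unpaired means nor excludes within-patient change. That stands: the point is about the rule the protocol does fix, and a reader should not infer that paired change has been ruled out.

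A reader might also infer that any improvement in the tables will be an artefact. The documents do not support this. They give no exit rate and no link between leaving and severity, and the shift vanishes when there is no link. What can be said is that death is one of the exit routes, and in a disease that section 8.1 calls progressive it is unlikely to be independent of these markers.

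The NT-proBNP range is a limit for data entry and review, not an expected distribution. It shows what the database will accept, not that extreme values will occur.

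The rule should not be stretched to serum free light chains. Table 1 lists them as baseline laboratory parameters, neither red flag nor functional outcome, so the sentence in 8.7 does not clearly reach them.

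The protocol does contain safeguards. It reports missing counts, reviews outliers and atypical values, concedes in section 8.9 that patients who are lost or do not complete treatment may be under-represented, and disclaims robust causal conclusions. These disclose the risk without correcting it. Counts are promised per variable rather than per quarter, and no rule for handling outliers is given.

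**Conclusion.** The point holds as a weakness in the stated method, not as a demonstrated bias. Section 8.7 allows for unequal follow-up when it sets event rates per patient-year and uses Kaplan–Meier for survival, but makes no such provision for the clinical and functional outcomes. Available-case means at successive quarters cannot by themselves show change within patients, which is what section 8.1 wants from the design.

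The size is unknown: about zero if exit is unrelated to severity, and roughly 0.15 to 0.33 SD at 18 to 24 months under a 25% yearly exit rate and hazard ratios of 1.5 to 2 per SD. A lower exit rate gives proportionately smaller shifts.

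That mean (SD) alone is a poor summary for NT-proBNP and troponin follows from the rule as written, although the percentages for NT-proBNP rest on the assumed distribution. That KCCQ would be reported as proportions is the natural reading of Table 1 together with section 8.7, but it is an inference. This is a worthwhile, inexpensive improvement to a secondary objective. The primary objective is unaffected.

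**What to change.** In section 8.7, or in the SAP with a pointer from 8.7:

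- For each quarter, report the number of patients contributing, the within-patient change from the baseline value (index value for the 6-minute walk test and KCCQ) in patients with both values, and those same patients' baseline or index value.
- For NT-proBNP and troponin, add median (IQR) or the geometric-mean ratio to baseline. Mean (SD) can stay alongside.
- In Table 1, retype KCCQ as a continuous score.

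No fixed minimum number per quarter is needed. Showing n lets the reader judge the late quarters.

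The cost is a few lines of text, one table correction and extra table columns. No new data are required and the study stays descriptive. Data collection is planned to run to 30 June 2026 and the final report is due on 31 December 2026, so the change can be made before analysis.

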8.8. Quality Control

Before the study launch, study personnel will review data collection and processing procedures, with all study-related trainings recorded in a training log.

The principal investigator and a designated CRO team will monitor the study data for accuracy and completeness, conducting periodic reviews to ensure adherence to the study protocol, quality of data collection, and completeness of datasets, following SOPs for all aspects of data collection, entry and data analysis consistency and reliability. The analytic dataset consisting of the collected data will be validated by the principal Investigator or designee who will verify the following:

- Review of illogical data or atypical values (incl. the values out of range and with different units/ information of what is indicated in Table 1. Variables of interests);
- Verification of conflicting data;
- Review of very high percentages of response as “not known” or “data not available”;
- Verification of accuracy of the collected data by comparison with the source documents.

CRO is responsible for following their own SOPs as well as Pfizer’s SOPs to ensure data quality and integrity, including archiving of statistical programs, appropriate documentation of data cleaning and validation of derived variables. Guidelines for data collection and data quality checks will be described in the Monitoring and Data Quality Oversight Plan.

A record of data quality problems and resolutions will be kept through documented meeting minutes.

All inconsistencies and/or data quality issues will be documented. Revisions of study documents will be noted in order to capture the change made, the change date, identification of the individual making

the change, as well as noting any further actions to be taken to identify and/or resolve additional data quality problems of this type.

Electronic Data will be stored in a secure, password-protected database with restricted access in compliance with all local applicable laws and regulations, with regular backups to prevent loss, physical paper version records will be stored in a locked, secure location accessible only to authorized personnel. Statistical programming and datasets used to generate study results will be archived with version control, ensuring reproducibility of analyses.

Data collection and processing will be limited to necessary data for study objectives, with data pseudonymized to protect participant privacy.

Statistical analysis scripts and programming used for the study will be independently reviewed by a biostatistician for accuracy and compliance with study objectives. All statistical code and datasets will be archived and available for audit as required.

8.9. Strengths and Limitations of the Research Methods

This study will provide insights into the clinical outcomes of ATTR-CM patients treated with tafamidis in Turkey. This localized focus on a unique population adds to the limited data on regional variations in the disease and treatment outcomes.

This study will have several limitations. Being a single-center study, the findings may not be generalizable to other centers, regions, or healthcare systems with different patient populations and practices. Medical records may have missing or incomplete information (e.g., certain biomarkers, imaging results, or medication adherence data).

Ascertainment of CHF hospitalization will be done by a principle investigator using all available records; potential misclassification of the reasons for hospitalizations is possible. To partially address the issue of misclassification, all CV hospitalizations will be captured and recorded in CRF as well. Emergency admissions for causes other than CHF will not be captured and analyzed. There is a potential, that some of the emergency admissions could be related to cardio-vascular causes, but full verification may not be possible; this will remain a limitation of the current study.

Only patients diagnosed and treated at the single participating center will be included, which could lead to a selection bias. Patients lost to follow-up or those who did not complete tafamidis treatment may not be fully represented.

The design of the study does not include a comparative arm and does not allow for robust causal conclusions related to tafamidis treatment effectiveness or safety.

